6.6.1. Dosing Interruptions

Appropriate follow-up assessments should be done until adequate recovery occurs as assessed by the investigator. Doses may be held up to 4 weeks until toxicity resolution. Depending on when the AE resolved, a treatment interruption may lead to the participant missing one or more of the subsequent planned doses.

Criteria required before treatment can resume are described in Dose Delays (Section 6.6.2), ISR [Section 8.2.10](#), IRRs ([Appendix 15](#)) or in the specific toxicity management guidelines for CRS ([Appendix 9](#)), and irAEs ([Appendix 14](#)).

The need for a dose reduction at the time of treatment resumption should be based on the criteria defined in [Section 6.6.3](#), unless expressly agreed otherwise following discussion between the investigator and the sponsor.

In the event of a treatment interruption lasting >4 weeks, treatment resumption will be decided in consultation with the sponsor.

6.6.2. Dose Delays

Re-treatment following treatment interruption for treatment-related toxicity may not occur until all of the following parameters have been met:

- ANC $\geq 1,000/\text{mm}^3$.
- Platelet count $\geq 50,000/\text{mm}^3$
- Nonhematologic toxicities have returned to baseline or Grade ≤ 1 severity (or, at the investigator's discretion, Grade ≤ 2 if not considered a safety risk for the participant).

If a treatment delay results from worsening of hematologic or biochemical parameters, the frequency of relevant blood tests should be increased as clinically indicated.

If these conditions are met within 4 weeks of treatment interruption, PF-07209960 may be resumed. Refer to the Section 6.6.3 for AEs requiring dose reduction at the time of treatment resumption.

If participants require discontinuation of PF-07209960 for more than 4 weeks from last dose (2 missed dose) at any time during the study, then study treatment should be permanently discontinued, unless the investigator's benefit/risk assessment suggests otherwise after discussion with the sponsor's medical monitor.

If a treatment interruption continues beyond Day 28 of the current cycle, then the day when treatment is restarted will be counted as Day 1 of the next cycle.

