6.6. Dose Modification

Every effort should be made to administer study intervention on the planned dose and schedule. In the event of significant toxicity, dosing may be delayed and/or reduced as described below. In the event of multiple toxicities, dose modification should be based on the worst toxicity observed. Participants are to be instructed to notify investigators at the first occurrence of any adverse symptom.

In addition to dose modifications, investigators are encouraged to employ best supportive care according to local institutional clinical practices.

Toxicities potentially related to PF-07209960 should be managed according to the dose modifications described in [Table 4](#).

Selected toxicities that do not resolve or worsen following supportive care and dose modifications and with a clinical presentation consistent with a potential irAE without a clear alternative explanation, may require treatment with corticosteroids or other immunosuppressants and should be managed according to the management of irAEs as described in [Appendix 14](#).

CRS should be managed according to the CRS Mitigation and Management guidance as described in [Appendix 9](#).

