Nonhematologic	Continue at the same dose level.	Continue at the same dose level.	Withhold dose until toxicity is Grade ≤ 1 , or has returned to baseline, then resume treatment at the same dose level or reduce the dose by 1 level at the discretion of the investigator*.	Withhold dose until toxicity is Grade ≤ 1 , or has returned to baseline, then reduce the dose by 1 level and resume treatment, or discontinue at the discretion of the investigator*.
Hematologic (except lymphopenia)	Continue at the same dose level.	Continue at the same dose level.	Withhold dose until toxicity is Grade ≤ 2 , or has returned to baseline, then resume treatment at the same dose level**.	Withhold dose until toxicity is Grade ≤ 2 , or has returned to baseline, then reduce the dose by 1 level and resume treatment**.

* Nausea, vomiting, or diarrhea must persist at Grade 3 or 4 despite maximal medical therapy to require dose modification.

** Cycle will not be extended to cover for the missing doses.

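### Protocol Section 6.6.2 and Table 4 set different recovery grades for re-dosing after a Grade 3 or 4 non-hematologic toxicity, the text does not settle which governs, and the ISR and CRS pointers lead to no criteria

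*Protocol*

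**What the plan says.** Five parts of the Protocol bear on when dosing may restart.

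- **Section 6.6** gives the general instruction: "Toxicities potentially related to PF-07209960 should be managed according to the dose modifications described in" Table 4.
- **Section 6.6.1** splits the question. On timing: "Criteria required before treatment can resume are described in Dose Delays (Section 6.6.2" and in four other places, namely Section 8.2.10 for injection site reactions (ISR), Appendix 15 for infusion reactions, "or in the specific toxicity management guidelines for CRS" (Appendix 9), and Appendix 14 for immune-related events. On dose: "The need for a dose reduction at the time of treatment resumption should be based on the criteria defined in" Section 6.6.3.
- **Section 6.6.2** covers any interruption for treatment-related toxicity. Its non-hematologic condition is baseline or Grade ≤1 or, at the investigator's discretion, "Grade ≤ 2 if not considered a safety risk for the participant". If the conditions are met within four weeks, dosing may restart.
- **Table 4 (Section 6.6.3)**, non-hematologic row. Grade 3: "Withhold dose until toxicity is Grade ≤ 1 , or has returned to baseline, then resume treatment at the same dose level", or one level lower if the investigator chooses. Grade 4: the same recovery grade, "then reduce the dose by 1 level and resume treatment, or discontinue at the discretion of the investigator". A footnote limits the row: "Nausea, vomiting, or diarrhea must persist at Grade 3 or 4 despite maximal medical therapy to require dose modification".
- **Section 6.6.3**, after a DLT: restart at the next lower level, if the investigator and sponsor judge that the participant is benefiting, once recovery is adequate. No grade is attached.

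**The concern.** This is a first-in-human study of an immune agonist, and the rule for giving the next dose after a severe toxicity should read one way. Here a participant whose Grade 3 event has settled to Grade 2 may be dosed under one section and must be held under another.

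The sponsor's opinion that Section 6.6.3 requires after a DLT would damp this, and most in-scope events in the Part 1 DLT window are DLTs under Section 4.3.3. But that check attaches to DLT events only. It does not reach:

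- events excepted from the DLT definition, such as Grade 3 fatigue controlled to Grade ≤2 within 72 hours;
- Part 1 events after the 28-day window, unless they are reclassified as DLTs;
- Part 2, because DLT monitoring is confined to Part 1.

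ISR and CRS are both adverse events of special interest (Section 8.3.8). For them, a site that follows Section 6.6.1 finds no criterion and falls back on the two conflicting rules.

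**Working it through.** **Step 1: scope.** Events with a specific rule drop out: immune-related events (Appendix 14), infusion reactions (Appendix 15, where Grade 3 or 4 means permanent discontinuation), QTcF prolongation (its own hold and restart rule in Section 8.2.3), and nausea, vomiting or diarrhea that the Table 4 footnote exempts. What remains is other treatment-related Grade 3 or 4 non-hematologic toxicity.

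**Step 2: the rules side by side.**

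| | Section 6.6.2 | Table 4 |
|---|---|---|
| Non-hematologic, after Grade 3 | Grade ≤1 or baseline; Grade ≤2 by discretion | Grade ≤1 or baseline |
| Non-hematologic, after Grade 4 | the same | Grade ≤1 or baseline |
| What discretion covers | the recovery grade | the dose level (Grade 3); reduce or discontinue (Grade 4) |
| Platelets | ≥50,000/mm³ | Grade ≤2 |

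The non-hematologic rows conflict. The platelet row does not: Section 4.3.3 puts Grade 3 thrombocytopenia below 50,000, so the two thresholds coincide.

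**Step 3: precedence.** Section 6.6 favours Table 4. Section 6.6.1 favours 6.6.2 for timing and 6.6.3 for dose, and 6.6.3 introduces Table 4 as recommended dose reductions. Yet the Table 4 cells state their own timing condition. No sentence resolves this. Letting 6.6.2 control also gives an odd result: under 6.6.3, recurrent intolerable Grade 2 toxicity restarts at the lower dose only after recovery to Grade ≤1 or baseline, while a Grade 4 event could restart at Grade 2.

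**Step 4: the pointers.** Section 6.6.1 names five places. Three hold resumption criteria: 6.6.2, Appendix 14 and Appendix 15. Two do not: Section 8.2.10 covers assessment, recording and referral of injection site reactions, and Appendix 9 covers CRS grading and treatment. The CRS text in Section 8.2.9 concerns release from observation, not the next dose.

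**Step 5: doses affected.** Inputs: dosing on Days 1 and 15 of a 28-day cycle, so doses fall due 14 and 28 days after the last one, and a visit window of ±2 days for these visits (Schedule of Activities). The latest in-window days are 14 + 2 = 16 and 28 + 2 = 30. Take an event that reached Grade 3, is still at Grade 2 and above baseline on day 14, and reaches Grade ≤1 on day R.

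| R (days after last dose) | Table 4 | 6.6.2, discretion used |
|---|---|---|
| 15–16 | dose late but within window | none need be held |
| 17–30 | one dose delayed beyond window or missed | none need be held |
| >30 | day-14 and day-28 doses both held beyond window | none need be held |

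Long holds reach the sponsor anyway. Past four weeks, 6.6.1 requires consultation with the sponsor, and 6.6.2 calls for permanent discontinuation unless a benefit/risk view, discussed with the medical monitor, says otherwise. Counted from the last dose, four weeks end on day 28. Counted from the first held dose (an assumption), they end on day 14 + 28 = 42.

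**Step 6: planned numbers.** Part 2 runs from 60 (three cohorts, minimum) to 90 + 60 = 150. With 14–22 in Part 1, the totals are 14 + 60 = 74 and 22 + 150 = 172, matching Section 9.2. So 60–150 planned participants lie in the part with no DLT check.

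**The case against.** The best reply is that the specific rule beats the general one. Section 6.6.2 is worded as a minimum, Table 4 is grade-specific, and Section 6.6 says to manage related toxicities by it. A site that follows Table 4 also meets the 6.6.2 non-hematologic condition, so nobody is forced to breach either rule. This reading is plausible, and it stands as one way to read the text. It does not close the matter, because 6.6.1 names 6.6.2 as the source of the criteria for resuming, and 6.6.2 goes on to give permission to restart.

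A second reply is that 6.6.2 applies only once there has been an interruption. SAP Section 6.8.5 defines a dose interruption as a planned dosing day with 0 mg given. On that definition only Table 4 speaks on day 14. But it is a definition for exposure summaries, and the conflict would still begin as soon as that dose was held.

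Third, the residue is narrow. Appendix 14 has a broad catch-all for suspected immune-related events, the 6.6.2 discretion carries its own safety-risk condition, and Section 8 requires safety issues to be discussed with the sponsor. For CRS, ASTCT Grade 2 means hypotension or low-flow oxygen, so the discretion would rarely be usable. All of this stands and limits the hazard.

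A reader might infer that the DLT check protects every Part 1 participant. It does not: it covers DLT events, and Part 1 events that are not DLTs fall outside it.

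**Conclusion.** The conflict is in the text and should be fixed at the next amendment. Two sections give different recovery grades for re-dosing after a related Grade 3 or 4 non-hematologic toxicity with no rule of its own, precedence is not settled, the DLT sentence gives no grade, and two of five resumption pointers are empty.

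The consequence is possible inconsistent re-dosing between sites. In the worked case the difference ranges from a late dose within window to two doses held beyond window. That rests on two assumptions: that recovery follows the stated pattern, and that a dose coming due during unresolved toxicity counts as an interruption under 6.6.2.

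A reader might infer that participants will be harmed. The documents give no frequency for such events and no outcome after re-dosing at Grade 2, so harm is not shown. A reader might also infer a biased MTD, since Section 4.3.3 requires two Cycle 1 doses for a participant without a DLT to be evaluable, and a held Day 15 dose could therefore lead to replacement. That route exists, but nothing in the documents gives its size, so no effect on the MTD is claimed.

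**What to change.** Add to Section 6.6.2:

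> After a Grade 3 or 4 non-hematologic toxicity, including a non-hematologic DLT, the Table 4 recovery grade (Grade ≤1 or baseline) and the Table 4 footnote apply; the Grade ≤2 discretion applies only to other toxicities that did not exceed Grade 2. Where Appendix 14, Appendix 15 or Section 8.2.3 gives a specific rule, that rule applies instead.

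In Section 6.6.1, point ISR to this rule instead of Section 8.2.10, and replace the CRS pointer with:

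> After CRS of any grade, dosing may resume only once CRS has fully resolved (no fever, hypotension or hypoxia attributable to CRS).

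Do not use ASTCT Grade ≤1 as the CRS threshold. ASTCT Grade 1 is active CRS, with temperature at or above 38°C (Appendix 9, Table 7), so that wording would allow re-dosing during ongoing CRS fever.

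The change is wording only and adds no procedures or participants. Its cost is that some participants with persistent Grade 2 toxicity after a Grade 3 or 4 event will have doses delayed or missed.

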6.6.3. Dose Reductions

Following dosing interruption or cycle delay due to toxicity, the PF-07209960 dose may need to be reduced when treatment is resumed.

No specific dose adjustments are recommended for Grade 1/2 treatment-related toxicity. However, participants experiencing recurrent and intolerable Grade 2 toxicity may resume dosing at the next lower dose level based on investigator's medical judgment once recovery to Grade ≤ 1 or baseline is achieved.

Dose reduction of PF-07209960 by 1 dose level (with maximum reduction to dose level -1, 0.3 mg SC, 0.06 mg IV) ([Table 2](#)) will be allowed depending on the type and severity of toxicity encountered. Participants requiring more than 1 dose reduction will be discontinued from the treatment and entered into the follow-up phase, unless otherwise agreed between the investigator and the sponsor. All dose modifications/adjustments must be clearly documented in the participant's source notes and CRF.

Once a dose has been reduced for a given participant, all subsequent cycles should be administered at that reduced dose level, unless further dose reduction is required. Intraparticipant dose re-escalation may be allowed after discussion between the investigator and sponsor. Participant must not experience a Grade 2 or higher adverse event to be eligible for intraparticipant dose re-escalation.

Table 3. Available Dose Reduction Levels From Starting Dose

Dose Level ^a	SC	IV ^b
Starting	CC1	

a. PF-07209960 dose de-escalation below -1 dose level is not allowed.

b. IV infusion over 1 hour (± 10 minutes)

Participants experiencing a DLT may resume dosing at the next lower dose level (if applicable) once adequate recovery is achieved, and in the opinion of the investigator and sponsor, the participant is benefiting from therapy.

For management of immune-related adverse events, please refer to [Appendix 14](#). For all other toxicities, recommended dose reductions for study intervention are described in Table 4.

Table 4. Treatment Dose Modifications for Study Intervention-Related Toxicity

Toxicity	Grade 1	Grade 2	Grade 3	Grade 4
Nonhematologic	Continue at the same dose level.	Continue at the same dose level.	Withhold dose until toxicity is Grade ≤ 1 , or has returned to baseline, then resume treatment at the same dose level or reduce the dose by 1 level at the discretion of the investigator*.	Withhold dose until toxicity is Grade ≤ 1 , or has returned to baseline, then reduce the dose by 1 level and resume treatment, or discontinue at the discretion of the investigator*.
Hematologic (except lymphopenia)	Continue at the same dose level.	Continue at the same dose level.	Withhold dose until toxicity is Grade ≤ 2 , or has returned to baseline, then resume treatment at the same dose level**.	Withhold dose until toxicity is Grade ≤ 2 , or has returned to baseline, then reduce the dose by 1 level and resume treatment**.

* Nausea, vomiting, or diarrhea must persist at Grade 3 or 4 despite maximal medical therapy to require dose modification.

** Cycle will not be extended to cover for the missing doses.

6.7. Intervention After the End of the Study

No intervention will be provided per protocol to study participants beyond the end of the study. Availability of PF-07209960 following closure of the study through expanded access/compassionate/continued use mechanism if the investigator and participant desire to continue treatment would be at the discretion of the sponsor and subject to local conditions and regulations.

7. DISCONTINUATION OF STUDY INTERVENTION AND PARTICIPANT DISCONTINUATION/WITHDRAWAL

7.1. Discontinuation of Study Intervention

In rare instances, it may be necessary for a participant to permanently discontinue study intervention (definitive discontinuation). Reasons for definitive discontinuation of study intervention may include the following:

- Objective disease progression;
- Global deterioration of health status requiring discontinuation;
- Unacceptable toxicity;
- Pregnancy;
- Significant protocol violation;
- Lost to follow-up;

- Participant refused further treatment;
- Study terminated by sponsor;
- Death.

Note that discontinuation of study intervention does not represent withdrawal from the study. If study intervention is definitively discontinued, the participant will remain in the study to be evaluated for long-term safety follow-up and survival. See the [SoA](#) for data to be collected at the time of discontinuation of study intervention and follow-up for any further evaluations that need to be completed.

In the event of discontinuation of study intervention, it must be documented on the appropriate CRF/in the medical records whether the participant is discontinuing further receipt of study intervention or also from study procedures, posttreatment study follow-up, and/or future collection of additional information.

7.2. Participant Discontinuation/Withdrawal From the Study

A participant may withdraw from the study at any time at his/her own request. Reasons for discontinuation from the study may include:

- Completed study follow-up;
- Study terminated by sponsor;
- Lost to follow-up;
- Refused further follow-up;
- Death.

At the time of discontinuing from the study, if possible, an early discontinuation visit should be conducted. See the [SoA](#) for assessments to be collected at the time of study discontinuation and follow-up and for any further evaluations that need to be completed.

If a participant withdraws from the study, he/she may request destruction of any remaining samples taken and not tested, and the investigator must document any such requests in the site study records and notify the sponsor accordingly.

If the participant withdraws from the study and also withdraws consent (see Section 7.2.1) for disclosure of future information, no further evaluations should be performed and no additional data should be collected. The sponsor may retain and continue to use any data collected before such withdrawal of consent.

Lack of completion of all or any of the withdrawal/early termination procedures will not be viewed as protocol deviations so long as the participant's safety was preserved.

7.2.1. Withdrawal of Consent

Participants who request to discontinue receipt of study intervention will remain in the study and must continue to be followed for protocol-specified follow-up procedures. The only

exception to this is when a participant specifically withdraws consent for any further contact with him or her or persons previously authorized by the participant to provide this information. Participants should notify the investigator in writing of the decision to withdraw consent from future follow-up, whenever possible. The withdrawal of consent should be explained in detail in the medical records by the investigator, as to whether the withdrawal is only from further receipt of study intervention or also from study procedures and/or posttreatment study follow-up, and entered on the appropriate CRF page. In the event that vital status (whether the participant is alive or dead) is being measured, publicly available information should be used to determine vital status only as appropriately directed in accordance with local law.

7.3. Lost to Follow-up

A participant will be considered lost to follow-up if he or she repeatedly fails to return for scheduled visits and is unable to be contacted by the study site.

The following actions must be taken if a participant fails to return to the clinic for/attend a required study visit:

- The site must attempt to contact the participant and reschedule the missed visit as soon as possible and counsel the participant on the importance of maintaining the assigned visit schedule and ascertain whether or not the participant wishes to and/or should continue in the study.
- Before a participant is deemed lost to follow-up, the investigator or designee must make every effort to regain contact with the participant (where possible, 3 telephone calls and, if necessary, a certified letter to the participant's last known mailing address or local equivalent methods). These contact attempts should be documented in the participant's medical record.
- Should the participant continue to be unreachable, he/she will be considered to have withdrawn from the study.

8. STUDY ASSESSMENTS AND PROCEDURES

The investigator (or an appropriate delegate at the investigator site) must obtain a signed and dated ICD before performing any study-specific procedures.

Study procedures and their timing are summarized in the [SoA](#). Protocol waivers or exemptions are not allowed.

Safety issues should be discussed with the sponsor immediately upon occurrence or awareness to determine whether the participant should continue or discontinue study intervention.

Adherence to the study design requirements, including those specified in the [SoA](#), is essential and required for study conduct.

All screening evaluations must be completed and reviewed to confirm that potential participants meet all eligibility criteria. The investigator will maintain a screening log to record details of all participants screened and to confirm eligibility or record reasons for screening failure, as applicable.

Procedures conducted as part of the participant's routine clinical management (eg, blood count) and obtained before signing of the ICD may be utilized for screening or baseline purposes provided the procedures met the protocol-specified criteria and were performed within the time frame defined in the [SoA](#).

Every effort should be made to ensure that protocol-required tests and procedures are completed as described. However, it is anticipated that from time to time there may be circumstances outside the control of the investigator that may make it unfeasible to perform the test. In these cases, the investigator must take all steps necessary to ensure the safety and well-being of the participant. When a protocol-required test cannot be performed, the investigator will document the reason for the missed test and any corrective and preventive actions that he or she has taken to ensure that required processes are adhered to as soon as possible. The study team must be informed of these incidents in a timely manner.

For samples being collected and shipped, detailed collection, processing, storage, and shipment instructions and contact information will be provided to the investigator site prior to initiation of the study.

